A sample protocol for this pilot study is shown in the Figure above. On Day 1 (lab visit #1) subjects will complete questionnaires, receive a wrist activity monitor, and a Personal Data Assistant (PDA; electronic diary) to record their daily pain, mood, sleep, and substance use (alcohol, caffeine, prescribed and over the counter medication, heating pads, ice packs, etc) while they sleep ad lib at home, following their usual sleep schedule. They will then undergo pain sensitivity testing (acute pain induction with forearm ischemia and heat, between noon-1pm as per our pilot). On Day 8 (lab visit #2) subjects will complete questionnaires, have their diaries and wrist actigraphy data reviewed and then will undergo pain sensitivity testing again. Following this subjects will be trained in home saliva collection, receive a kit to take home and will complete their saliva collection that night. The following morning (Day 9, home visit #1) two research staff (mixed gender team) will visit the subject in their home to set up and instruct the subjects in the bright light treatment, and collect their saliva kit and samples. Subjects will self-administer the bright light for 1 h/morning for 6 days before returning to the lab (Day 15, lab visit #3) for repeat questionnaires, review of their diaries and wrist actigraphy, pain sensitivity testing and issuing of the saliva collection kit. Research staff will again visit their homes to collect the saliva kit and samples (Day 16, home visit #2). After a further 7 days of bright light treatment, subjects will return for their last lab visit (Day 22, lab visit #4) for questionnaires, review of their diaries and wrist actigraphy, repeat pain sensitivity testing and issuing of the saliva collection kit. The following morning on Day 23 another home visit (home visit #3) will occur, and research staff will collect the light boxes, saliva kit, samples, and wrist monitors. The PDAs for electronic diaries will be left with the subject. During a 1 month follow up after cessation of the bright light treatment, subjects will continue to report their pain, mood and sleep once a day on the electronic diaries (once a day only to reduce burden and improve compliance). At the end of the follow up staff will collect the PDAs with electronic diaries during a final home visit.

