Bright Light Treatment At Home To Manage Chronic Pain In U.S. Veterans

NCT02373189

Document Date: 12/23/22

Data Analysis

Aim 1. To determine the feasibility and acceptability of bright light treatment in a sample of US veterans (n=30) experiencing chronic low back pain. For Aim 1 we will track the number of US veterans who express interest in the study, the number that meet our inclusion criteria, the number that enroll, the number of mornings that bright light is self-administered and the duration of the exposure, and we will collect treatment expectancy and treatment satisfaction ratings. Hypothesis 1: We expect reasonable feasibility in that (i) we will be able to enroll 2 US veterans per month, (ii) $\geq 75\%$ of those enrolled self-administer at least 30 mins of morning bright light on at least 50% of treatment days (this light should still be somewhat effective, as per winter depression studies [125, 126, 131]). Research Strategy Page 54 Contact PD/PI: [name] Hypothesis 2: We expect reasonable acceptability in that (i) at least 1 in 4 US veterans who are eligible for the study agree to participate, (ii) average expectancy rating at start of bright light treatment is $\geq 6/10$, (iii) the attrition rate is $\leq 30\%$, and (iv) average treatment satisfaction at end of bright light treatment is $\geq 6/10$. Aim 2. To examine the effects of 6 days and 13 days of bright light treatment on chronic pain intensity and sensitivity in US veterans (improved PTSD symptoms, mood and sleep are secondary outcomes).

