For Aim 2 we will plot daily diary ratings of pain intensity expressed as percentage change from baseline pain intensity (mean intensity over the 7 days of baseline). The point where the mean change for the whole sample achieves 30% (“moderately clinically meaningful effect” p.239, [137]) will reveal a potential candidate for an optimal treatment dose. We will also examine pain sensitivity (ischemia, heat) changes over the 4 lab visits. Hypothesis 3: We expect (i) a $\geq 30\%$ reduction in pain intensity ratings and (ii) a $\geq 30\%$ reduction in pain sensitivity (ischemia and thermal pain) by the 13th day of morning bright light treatment. As a preliminary analysis, we will examine these data with a within-subjects ANOVA to determine: a) effect size of change over 13 days of treatment; b) statistical significance of this change; c) whether there is significant non-linearity indicating that response to treatment reached a plateau. In an effort to understand a plateau effect, we will use a piecewise linear mixed model with a fixed change point occurring at the 30% change level. Random effects for time before the change point and time after change point will be included in the model. We will use graphical analyses to investigate violations of the model assumption. Secondary analyses for daily ratings of mood and sleep will be conducted similarly. For additional secondary analyses involving PTSD, depressive and anxiety symptoms, and sleep questionnaires, we will subject data to within-subjects ANOVAs to determine: a) effect sizes of changes over 13 days of treatment; b) statistical significance of these changes; c) whether there is significant non-linearity indicating that treatment response plateaued.

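### Pain sensitivity has no named reference visit, and the four visits include an untreated week; if Day 1 enters the ANOVA, significant non-linearity cannot be read as a plateau

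*SAP*

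**What the plan says.** The Protocol's visit schedule tests pain sensitivity at four lab visits. The first is Day 1. On Day 8 subjects complete questionnaires and data review "and then will undergo pain sensitivity testing again". Light is set up at home on Day 9. The Day 15 and Day 22 tests follow 6 and 13 days of light.

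The SAP (Data Analysis, Aim 2) states the aim as "To examine the effects of 6 days and 13 days of bright light treatment" on pain intensity and sensitivity. Diary pain has a defined baseline, the mean over the seven baseline days. Pain sensitivity has only this: "We will also examine pain sensitivity (ischemia, heat) changes over the 4 lab visits". Hypothesis 3(ii) expects a reduction of at least 30%, described as "reduction in pain sensitivity (ischemia and thermal pain) by the 13th day of morning bright light treatment", without saying from which visit.

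The SAP continues: "As a preliminary analysis, we will examine these data with a within-subjects ANOVA". The targets include "effect size of change over 13 days of treatment" and "whether there is significant non-linearity indicating that response to treatment reached a plateau".

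**The concern.** Two phrases in the same paragraph point to different sets of visits. Four lab visits include Day 1 and the untreated week that follows it. Thirteen days of treatment describes Day 8 to Day 22. Nothing reconciles them, and an analyst could follow either.

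The choice matters because of how the ANOVA is to be read. Over four visits, a response that begins only after Day 8 is flat and then falls. That profile is bent at the start of treatment whether or not the response later levels off, so non-linearity is no longer specific to a plateau. Any change between Days 1 and 8, for example from familiarity with the test, also enters a time effect that is described as change over treatment. Separately, the 30% target has no stated denominator, so the reference could be chosen after the data are seen.

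**Working it through.** **Inputs from the documents.** Tests on Days 1, 8, 15 and 22; light from Day 9; n=30; a 30% target. The documents give no SD, no size of untreated change and no form of non-linearity test, so there is no planned figure to reproduce.

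**Assumptions.** Day 1 mean = 100 on a scale where lower means less sensitive; independent visit errors with within-subject SD 15, 20 or 25; sphericity; two-sided alpha 0.05. Visit means are written as changes from Day 1. Triplets of results are for SD 15/20/25.

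**1. Shape over four visits.** Quadratic Q = (1,-1,-1,1); cubic C = (-1,3,-3,1).
- Steady response, no plateau (0,0,-15,-30): Q = 0 - 0 + 15 - 30 = -15; C = 0 + 0 + 45 - 30 = +15.
- Full plateau by Day 15 (0,0,-30,-30): Q = 30 - 30 = 0; C = 90 - 30 = +60.
- Untreated one-off fall, no treatment effect (0,-10,-10,-10): Q = 10 + 10 - 10 = +10.

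These values do not depend on the SD. The steady response has a quadratic component; the full plateau has none.

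**2. How often non-linearity is flagged over four visits.** The 2-df test (quadratic and cubic together) has non-linear sum of squares Q²/4 + C²/20, noncentrality n × SS / SD², and 2 and 58 df.
- Steady: SS = 225/4 + 225/20 = 67.5; noncentrality at SD 15 = 30 × 67.5/225 = 9.0. Flagged in 75/49/33%.
- Full plateau: SS = 3600/20 = 180; noncentrality at SD 15 = 24.0. Flagged in 99/90/73%.
- Partial flattening (0,0,-20,-30): Q = -10, C = +30, SS = 25 + 45 = 70. Flagged in 76/50/34%, almost the same as for the steady response.
- Quadratic term alone: steady 75/51/35%, full plateau 5%.

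**3. The same question on Days 8, 15 and 22.** Contrast (1,-2,1).
- Steady: 0 + 30 - 30 = 0, flagged in 5%.
- Full plateau: 0 + 60 - 30 = +30, flagged in 99/90/74%.

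**4. Time effect with no treatment effect.** For (0,-10,-10,-10) the mean is -7.5 and SS = 7.5² + 3 × 2.5² = 75. Noncentrality at SD 15 = 30 × 75/225 = 10, with 3 and 87 df. Significant in 74/47/31%. A 5% untreated change gives 22/14/11%. Without Day 1 the rate is 5%.

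**5. The 30% target.** Visit means 100, 90, 80, 70:
- from Day 1: (100 - 70)/100 = 30.0%
- from the Day 1/Day 8 mean: (95 - 70)/95 = 26.3%
- from Day 8: (90 - 70)/90 = 22.2%

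One data set meets or misses the target according to the reference.

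**The case against.** The strongest reply is that the SAP can be read sensibly as it stands. The ANOVA concerns 13 days of treatment and the aim names 6 and 13 days of light; both describe Days 8, 15 and 22. The data sent to the ANOVA may also be mainly the diary ratings. This stands as a limit: a reader might infer that the plan puts Day 1 into the treatment test, and the documents do not establish that. They leave it open. Pain sensitivity is named just before the ANOVA and is part of Hypothesis 3, so it cannot be assumed to be excluded.

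A second reply is that sign would protect the plateau reading: -15 is an accelerating fall, and a signed test would not call it a plateau. That is fair for the steady response, but the SAP states no sign rule. Sign would not recover the full plateau, whose quadratic is 0, and an untreated one-off fall gives +10, which looks like flattening.

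Third, a reader might infer that a four-visit test cannot tell a plateau from a steady response at all. That is too strong: the 2-df test flags a full plateau 24 to 41 percentage points more often. What survives is that a flag alone does not identify a plateau.

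Fourth, the illustration uses the full 30% effect. With a steady 15% response (0,0,-7.5,-15), the 2-df test flags only 24/15/11%.

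Finally, a reader might infer that the missing reference always alters the Hypothesis 3(ii) result. It does so only if the Day 1 and Day 8 means differ. The 30% figure is an expectation with no decision rule attached.

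**Conclusion.** The point holds in conditional form. The SAP names no reference visit for pain sensitivity and does not reconcile four lab visits with 13 days of treatment. If all four visits enter the ANOVA, non-linearity is not evidence of a plateau and untreated change counts in the time effect. If the Day 1 and Day 8 means differ, the reference can decide whether the 30% target is met.

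The contrast values rest only on the assumed visit means. The percentages also rest on the assumed SDs, sphericity and n=30, none of which except n comes from the documents.

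The consequence is minor to moderate. This is a pilot, the ANOVA is called preliminary, and a reader should not infer that the candidate treatment dose is affected: it comes from diary pain, whose baseline is defined. The point is still worth correcting because pain sensitivity is in the Aim 2 statement and has its own target.

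**What to change.** State in the SAP, for pain sensitivity:
- Day 8 (lab visit 2) is the reference for the 6-day effect, the 13-day effect and the 30% target.
- The treatment time effect and the non-linearity test use Days 8, 15 and 22 only.
- A plateau is claimed only if the second-week reduction is smaller than the first-week reduction.
- The Day 1 to Day 8 change is reported separately, with a 95% CI, as untreated change.

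This is a wording change; all four visits are already collected. It has three costs.
- **Precision.** The 95% CI half-width for Day 22 minus Day 8 is t × SD × √(2/30), with t = 2.045 on 29 df: 7.9/10.6/13.2 points. A Day 1/Day 8 mean reference gives t × SD × √(1.5/30) = 6.9/9.1/11.4. The ratio √(2/1.5) = 1.155, so the interval is about 15% wider. In return, a one-off 10% untreated change with no treatment effect is significant in 5% with Day 8, against 30/19/14% with the mean.
- **Power for partial flattening is low.** Day 8, 15 and 22 values of 0, -20, -30 give a contrast of 40 - 30 = 10, detected in 30/19/14%. A non-significant result should not be read as absence of a plateau.
- **Later drift remains.** A steady drift (0,-5,-10,-15) with no treatment effect still makes Day 22 minus Day 8 significant in 70/47/32%. Without a control group, no choice of reference allows the change to be attributed to light, and the SAP should say so.

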Aim 3. To determine time course of decay of treatment response (decreased pain intensity) after cessation of light treatment. For Aim 3, we will plot daily diary ratings of pain intensity expressed as percentage change from the mean of pain ratings over the last 3 days of bright light treatment. The point where the mean change for the whole sample achieves 20% (less than a “moderate” decrease [137]) will reveal a potential candidate time for a maintenance dose of bright light. Second, we will subject these data to a within-subjects ANOVA to determine: a) effect size of erosion over 4 weeks of follow-up; b) statistical significance of this change. A change point modeling strategy similar to Aim 2 will be used here, but the change point will be set at a 20% level rather than a 30% level. Secondary analyses involving daily diary ratings of sleep and mood will be conducted as described above. Hypothesis 1: A mean increase of 20% in pain ratings is expected to occur within the first week post treatment (as per winter depression studies [125, 126, 131]). Hypothesis 2: Pain intensity is expected to return to baseline by 1 month post treatment (as per winter depression studies [125, 126, 131]).

We will also examine effects of other factors on treatment response. We will determine whether analyses must be adjusted for confounding factors including but not limited to age, BMI, race/ethnicity, employment, physical workload, any comorbidity (including depression and anxiety), history of traumatic brain injury, time from onset of chronic pain, current psychotropic and analgesic medications, and other treatments being received for chronic pain and/or PTSD. These analyses may involve treating these factors as time-varying covariates. We will also determine whether key factors moderate treatment response. We plan to test whether men or women

and those with low vs. high psychiatric symptoms (e.g., PTSD) show evidence of differential treatment response. These analyses will involve testing Sex or Psychiatric Symptom x Time interactions on pain intensity during and following treatment. In other exploratory analyses we will examine the correlations between change in DLMO and DLMO to midpoint of sleep interval and change in pain, mood and sleep.

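### For daily diary ratings, the planned ANOVAs appear to compare light days (or follow-up days) only with one another, so their effect size and p value miss a change complete by the first day

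*SAP*

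**What the plan says.** SAP, Data Analysis, Aim 2, first defines the variable to be plotted: "daily diary ratings of pain intensity expressed as percentage change from baseline pain intensity (mean intensity over the 7 days of baseline". It adds the laboratory outcome: "We will also examine pain sensitivity (ischemia, heat) changes over the 4 lab visits". Then, as a preliminary analysis, "we will examine these data with a within-subjects ANOVA to determine: a) effect size of change over 13 days of treatment", together with its statistical significance and any non-linearity that would indicate a plateau. Daily mood and sleep ratings are to be handled in a similar way.

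Aim 3 re-expresses diary pain as percentage change from the mean of the last 3 light days. After the plot, "we will subject these data to a within-subjects ANOVA to determine: a) effect size of erosion over 4 weeks of follow-up", again with a significance test.

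Neither part lists the levels of the time factor, says whether the reference period is one of them, or says that mean change will be tested against zero. The planned sample is "US veterans (n=30) experiencing chronic low back pain", with no control arm described.

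**The concern.** Hypothesis 3(i) is about a fall from the baseline week, and the first Aim 3 hypothesis is about a rise from the end of light. With no control arm described, those reference periods are the only comparators for the diary. If each is used only to scale the ratings, the ANOVA on the scaled ratings answers another question: whether light days differ among themselves, or follow-up days among themselves.

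A 30% fall present from the first light day would satisfy Hypothesis 3(i), yet the ANOVA would give an effect size near zero and a non-significant p value. Complete loss of response on the first day off light would look like no erosion in the ANOVA. Effect size is a main product of a pilot study, and this ANOVA is the only stated source of an effect size and significance test for diary pain.

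**Working it through.** **Inputs from the documents.** n = 30. The attrition ceiling of 30% leaves 30 × 0.7 = 21. Light days: 6 + 7 = 13. Follow-up: 4 weeks = 28 days. Expected fall: 30% by light day 13. Expected decay: a 20% rise within week 1 and return to baseline by 1 month, which after a 30% fall is a rise of 1/0.7 − 1 = 42.9%. The plan gives no power, alpha or SD, so it has no figure to reproduce.

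**Step 1: what the time effect can see.** For k days with means μ_j, the noncentrality is λ = n Σ(μ_j − μ̄)² / σ². It is unchanged by any constant shift of the whole series.
- Aim 2, full fall on day 1: μ_j = −30 for all 13 days, so μ̄ = −30 and λ = 30 × 13 × 0² / σ² = 0.
- Aim 3, full loss on day 1: μ_j = +42.9 for all 28 days, so λ = 0.

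No assumed SD enters here. Dividing by a subject's own reference rescales that subject's series but leaves a flat series flat.

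**Step 2: what the effect size leaves out.** With half-life h days, the share of the response present on light day t is 1 − 0.5^(t/h).
- h = 1: day 1 share 0.50. Mean change is −15 on day 1 and about −30 on day 13, so the among-day change is about 15 of 30 points.
- h = 2: day 1 share 1 − 0.5^0.5 = 0.293. Mean change is −8.8 on day 1 and −29.7 on day 13, so the among-day change is 20.9 of 29.7 points, about 70%.

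**Step 3: rejection rates (simulation).** Assumed, not in the documents: two-sided alpha 0.05; baseline 6/10; between-subject SD 1.5; mean effect 0.3 × 6 = 1.8 points with subject SD 1.8; day-to-day SD 1.0 to 2.0 (Aim 2) or 1.0 to 1.5 (Aim 3); lag-1 correlation 0.3; Greenhouse-Geisser correction; 1,000 runs per setting. Ranges cover these SDs and n = 30 and 21. The contrast is the mean of all light (or follow-up) days minus the reference mean.

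| Course | ANOVA, light or follow-up days only | Contrast with reference |
|---|---|---|
| Aim 2, complete on day 1 | 2–4% | 95–100% |
| Aim 2, half-life 0.5 day | 4–19% | 95–100% |
| Aim 2, half-life 1 day | 13–78% | 95–100% |
| Aim 2, half-life 2 days | 30–96% | 92–100% |
| Aim 2, linear to day 13 | 54–99% | 78–100% |
| Aim 3, complete on day 1 | 1–2% | 96–100% |
| Aim 3, half-life 1 day | 12–62% | 95–100% |
| Aim 3, half-life 2 days | 42–94% | 95–100% |
| Aim 3, 20% at day 7, baseline at day 28 | 81–99% | 88–99% |

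A second set on the % scale (baseline 5/10, between-subject and day-to-day SD both 1.2, 30% mean fall with subject SD 20 points, same correlation) agrees. For Aim 2 at n = 30 the light-days-only ANOVA rejected in 3% (day-1 step), 31% (half-life 1 day), 70% (2 days) and 94% (linear). The last 3 light days against baseline gave about 99% throughout.

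**Step 4: adding the reference as levels (day-1 step, assumptions of Step 3).** One reference level gives 58–100% (Aim 2) and 60–99% (Aim 3). All 7 baseline days, or all 3 end-of-light days, give 91–100% in each.

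**Step 5: ischemia and heat.** These are measured on Days 1, 8, 15 and 22. On Day 8 subjects "then will undergo pain sensitivity testing again", and the light is set up on Day 9, so two of the four levels are untreated. A step of d residual SDs after Day 8 has λ = n × 4 × (d/2)². At d = 0.8 and n = 30 this is 30 × 0.64 = 19.2, with power 96% (86% at n = 21). At d = 0.5 power is 60% and 43%. A rapid change is visible there.

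**The case against.** The strongest reply is that the SAP never says the reference is excluded. Change over 13 days could mean baseline to day 13, and the baseline days sit in the same diary. That stands: a reader might infer that the ANOVAs certainly contain no untreated or end-of-light level, and the text does not establish this. But the variable as defined, the spans as named and the absence of any test against the reference make exclusion the natural reading.

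A reader might also infer that any fast response would test as no change. That is too broad. Near-nominal rejection applies only to a change essentially complete by the first day; over a few days the loss of power depends on the SDs, and the SAP's own expected decay, taken as in the table, is largely detectable.

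Nor does the point extend to all Aim 2 pain outcomes, since the four lab visits include untreated ones.

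It would also be wrong to say that adding the reference on the % scale cannot help because it is 0 for everyone. Differences from a constant level still vary: under the second set of assumptions, adding it raised Aim 2 day-1-step rejection to 93% at n = 30 and 72–77% at n = 21 (two runs), and Aim 3 to 70% at n = 30. Raw ratings are preferable, not essential.

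Finally, the plots with their 30% and 20% thresholds come first, would show a rapid change at once, and are the stated basis for the candidate timings; the Aim 2 ANOVA is called preliminary. That limits the harm to the effect size and p value. The piecewise model does not clearly recover these: no test of level against the reference is stated, and an immediate response leaves almost no segment before the change point.

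**Conclusion.** The concern holds for daily diary ratings of pain intensity, and for the mood and sleep ratings analysed the same way. On the natural reading, the Aim 2 and Aim 3 ANOVAs give an effect size and p value that do not measure change from the reference named in the hypotheses. They are blind to a change complete by the first day and understate one largely complete within the first day or two: about half the change is left out at a 1-day half-life and about 30% at 2 days.

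The zero noncentrality for a day-1 step needs no assumed SD, only that the levels exclude the reference. The shares left out assume exponential courses, and every rejection rate rests on assumed SDs, correlation and alpha. The documents do not support saying that the reference is definitely excluded, or that a rapid change would go unseen in the study as a whole.

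**What to change.** For each diary ANOVA, list the time levels and include the reference days: the 7 baseline days with the 13 light days for Aim 2, and the last 3 light days with the follow-up days for Aim 3. Use raw ratings for preference.

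Take the effect size and p value from prespecified contrasts: last light days minus baseline week (Aim 2), and each follow-up week minus the last 3 light days (Aim 3). Keep the among-day time effect to describe shape and plateau, and keep the percentage plots. Apply the same rule to daily mood and sleep.

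The cost is SAP wording and a little analysis work. The protocol already runs the diary from Day 1 through follow-up, so no new data are needed.

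### Significant non-linearity is taken as the sign of a plateau, but that test alone does not identify one; nothing corrects this for the questionnaires, and only part of it is corrected for the diary outcomes

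*SAP*

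**What the plan says.** The SAP, Data Analysis, Aim 2, introduces the test for pain with "As a preliminary analysis, we will examine these data with a within-subjects ANOVA to determine" three things. The third, item c), is "whether there is significant non-linearity indicating that response to treatment reached a plateau".

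For diary pain there is more. The daily course is plotted: "For Aim 2 we will plot daily diary ratings of pain intensity expressed as percentage change from baseline pain intensity". A model then follows: "In an effort to understand a plateau effect, we will use a piecewise linear mixed model with a fixed change point occurring at the 30%" (that is, where pain has changed by that amount). On its structure the SAP adds: "Random effects for time before the change point and time after change point will be included in the model". Daily mood and sleep follow the same route: "Secondary analyses for daily ratings of mood and sleep will be conducted similarly".

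The questionnaires are handled differently: "For additional secondary analyses involving PTSD, depressive and anxiety symptoms, and sleep questionnaires, we will subject data to within-subjects ANOVAs". Their item c) is "whether there is significant non-linearity indicating that treatment response plateaued", and no plot or follow-on model is named.

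Neither item c) names a contrast, a sign, or a condition on the change late in treatment. The Protocol schedules questionnaires on Days 1, 8, 15 and 22. Days 1 and 8 precede light, Day 15 follows 6 days of it, and Day 22 follows 13 days.

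**The concern.** Non-linearity means only that the mean course is not a straight line. Three quite different courses have that property: a fall that then levels off (plateau), no change followed by a fall (late start, still improving), and a fall followed by a partial return (fading). If significance is enough to report a plateau, the last two can be reported as the first.

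Aim 2 sets out to compare the effects of 6 and 13 days of light. A late start read as a plateau would suggest that the response was complete when it was still growing. A fading response read as a plateau would hide loss of effect during treatment. Either error would carry into how the time course is described when a later trial is designed.

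**Working it through.** The SAP gives no alpha, power or sample-size figure for the non-linearity test, so there is no figure of its own to reproduce. The check is in four steps.

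**1. Three visits (Days 8, 15, 22): signs, with no assumption about variance.** The days are equally spaced, so the curvature contrast is (+1, -2, +1). With change from Day 8 and improvement negative:

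- Plateau (0, -d, -d): 0 + 2d - d = +d.
- Late start, still improving (0, 0, -d): 0 - 0 - d = -d.
- Fading (0, -d, -f) with f < d: 2d - f, which exceeds +d.

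A two-sided test depends on the absolute value. Plateau and late start are therefore flagged equally often whatever the SD, correlation or sample size, and fading more often than either. The sign separates late start from plateau, but not fading from plateau.

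**2. Size for the questionnaires.** Assumptions, not from the documents: two-sided alpha 0.05, equal visit SDs, equal correlation r between visits, change of 0.6 SD, fading pattern 0/-0.6/-0.2 SD. From the SAP: n = 30.

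SD of the contrast = √[6(1 - r)], in SD units. Noncentrality = contrast × √n / SD of the contrast. Power is from the noncentral t with n - 1 df.

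| r | SD of contrast | Course | Contrast | Noncentrality | Flagged |
|---|---|---|---|---|---|
| 0.8 | √1.2 = 1.095 | plateau or late start | ±0.6 | 0.6 × 5.477 / 1.095 = 3.00 | 82.6% |
| 0.8 | 1.095 | fading | 1.2 - 0.2 = 1.0 | 5.477 / 1.095 = 5.00 | 99.8% |
| 0.6 | √2.4 = 1.549 | plateau or late start | ±0.6 | 0.6 × 5.477 / 1.549 = 2.12 | 53.6% |
| 0.6 | 1.549 | fading | 1.0 | 5.477 / 1.549 = 3.54 | 92.7% |

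**3. Adding Day 1.** With Days 1, 8, 15 and 22 the quadratic contrast is (+1, -1, -1, +1).

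- Step-and-hold plateau (0, 0, -d, -d): 0 - 0 + d - d = 0.
- Steady fall throughout treatment, by days of light (0, 0, -6d/13, -d): 6d/13 - d = -7d/13.

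A quadratic test now misses an exact plateau and can flag a steady response that has none. A cubic contrast (-1, +3, -3, +1) would pick up the step (3d - d = 2d), but it too is non-zero for the steady fall (18d/13 - d = 5d/13).

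**4. Diary outcomes.** A simulation of the quadratic test over 13 light days (4,000 runs per case) assumed a between-subject SD of 15 percentage points, a response multiplier with SD 0.5, and a residual SD of 15 or 25 points. The courses were: plateau, 30% by light day 6 and then flat; late start, no change to day 6 and then a straight fall to 30% at day 13; fading, 30% at day 6 and back to 10% at day 13. The range runs from n = 30 with residual SD 15 to n = 21 (30 less the 30% attrition limit) with residual SD 25:

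- plateau flagged in 99.9% to 73%;
- late start in 99% to 62%;
- fading in 100% to 97%.

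These percentages depend heavily on the assumed SDs and shapes. The signs of the contrast do not depend on the SDs.

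The piecewise model was then considered without noise. For the plateau, the slope after the 30% point is 0. For fading, pain rises by (30 - 10)/7 = 2.9 points a day. A late start that reaches 45% at day 13 falls by 45/7 = 6.4 points a day after first passing 30% on day 11. A late start that reaches 30% only on day 13 leaves no later segment to estimate.

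**The case against.** The strongest reply concerns diary pain. The ANOVA there is called preliminary, the daily course is plotted, and the piecewise model has separate time effects on either side of the change point. A fading response would show a rising later slope; a late start that continues past 30% would show a falling one. A reader might infer that every late or fading response will be reported as a plateau. The documents do not support that for diary pain, nor for daily mood and sleep, which follow the same strategy. What remains is narrower: no estimate or CI for the later slope is required, the model is introduced as a way to understand a plateau, and its change point sits at 30% change, not where the curve flattens.

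Second, item c) can be read restrictively, as meaning only the kind of non-linearity that indicates a plateau. That reading is fair, but the SAP does not say how that kind is recognised. Likewise, effect sizes are planned and three visit means would show the shape to a careful reader; but the SAP does not make the conclusion depend on them.

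Third, a reader might infer that the dose conclusion of Aim 2 rests on this test, or that a non-significant result will be taken as no plateau. Neither is in the documents. The dose candidate comes from the point where mean change reaches 30%, and the SAP attaches no conclusion to non-significance.

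**Conclusion.** The point stands in a limited form. Significant non-linearity in the planned ANOVA does not by itself identify a plateau, and for the three on-schedule visits this follows from the contrast alone. For the PTSD, depression, anxiety and sleep questionnaires nothing in the plan corrects it. For diary pain, mood and sleep it is partly mitigated.

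The questionnaire percentages rest on the assumed correlation, effect size and alpha, and the diary percentages on assumed SDs. They show that the wrong courses are flagged about as often as the right one, or more often; they do not predict this trial's error rate.

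What is affected is the time-course conclusion of Aim 2. The 30% dose-candidate rule and the feasibility thresholds are untouched. In a single-arm pilot of 30 this should be fixed, but it does not undermine the study.

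**What to change.** In both places, replace the non-linearity criterion with estimates and 95% CIs of two quantities:

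- early change: Day 15 minus Day 8;
- late change: Day 22 minus Day 15 for the questionnaires, and the slope over the second light week for the diary outcomes.

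Report a plateau only if the early change is an improvement and the late-change CI lies wholly within a pre-stated margin on both sides, so that meaningful further improvement and meaningful worsening are both excluded. A one-sided margin would not do, because a fading response would pass it. Otherwise report still improving, worsening or undetermined.

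The cost is SAP wording only; the data are already collected. The drawback is that the answer will sometimes be undetermined. Under the same assumptions, the late-change CI half-width is t × √[2(1 - r)/n]. For n = 30 this is 2.045 × 0.115 = 0.24 SD at r = 0.8, and 2.045 × 0.163 = 0.33 SD at r = 0.6. For n = 21 it is 2.086 × 0.138 = 0.29 SD and 2.086 × 0.195 = 0.41 SD. A margin narrower than the half-width could not support a plateau claim, so it should be chosen on clinical grounds with that limit in view.
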